6.3 IRINOTECAN (12/18/18)

[CPT-11, Camptothecin-11,7-ethyl-10-(4-[1-piperidino]-1-piperidino)-carbonyloxy-camptothecin], Camptosar®, NSC #616348

Source and Pharmacology:

Irinotecan is a semisynthetic water-soluble analog of camptothecin (a plant alkaloid isolated from *Camptotheca acuminata*). Irinotecan is a prodrug that requires conversion,

by the carboxylesterase enzyme to the topoisomerase-I inhibitor, SN-38 in order to exert anti-tumor activity. SN-38 is approximately 1000 times more potent than irinotecan. Camptothecins interact specifically with the enzyme topoisomerase I which relieves torsional strain in DNA by inducing reversible single-strand breaks. Irinotecan and its active metabolite SN-38 bind to the topoisomerase I-DNA complex and prevent religation of these single-strand breaks. Current research suggests that the cytotoxicity of irinotecan is due to double-strand DNA damage produced during DNA synthesis when replication enzymes interact with the ternary complex formed by topoisomerase I, DNA, and either irinotecan or SN-38. Renal excretion is a minor route of elimination of irinotecan. The majority of the drug is metabolized in the liver. SN-38 is conjugated to glucuronic acid and this metabolite has no anti-tumor activity. The extent of conversion of SN-38 to its glucuronide has been inversely correlated with the risk of severe diarrhea, because the other major route of SN-38 excretion is biliary excretion by canalicular multispecific organic anion transporter (cMOAT) which presumably leads to mucosal injury. In addition, APC and NPC are oxidative metabolites of irinotecan dependent on the CYP3A4 isoenzyme. After intravenous infusion of irinotecan in humans, irinotecan plasma concentrations decline in a multiexponential manner, with a mean terminal elimination half-life of about 6 to 12 hours. The mean terminal elimination half-life of the active metabolite SN-38 is about 10 to 20 hours. Irinotecan is 30% to 68% bound to albumin and SN-38 is approximately 95% bound to albumin.

Toxicity:

Incidence	Toxicities
Common (>20% of patients)	
• Anemia• Thrombocytopenia• Neutrophil count decreased• White blood cell count decreased• Nausea• Vomiting• Constipation• Anorexia• Fever• Asthenia• Cholinergic symptoms: (rhinitis, increased salivation, miosis, lacrimation, diaphoresis, flushing, and intestinal hyperperistalsis that can cause abdominal cramping and diarrhea)• Alopecia• Bilirubin increased• Mucositis• Dyspnea• Cough• Weight loss• Pain
Occasional (4-20% of patients)	
• Abdominal fullness• Flatulence• Vasodilation• Hypotension

	
• Dehydration• Edema• AST increased• Alkaline phosphatase increased• Ascites• Jaundice• Febrile neutropenia• Infection• Headache• Dizziness• Chills• Insomnia• Rash• Dyspepsia• Somnolence• Thromboembolic events• Pneumonia
Rare (≤ 3% of patients)	
• Anaphylaxis• Bradycardia• Disorientation/confusion• Colitis• Renal failure (secondary to severe dehydration)• Ileus• Pancreatitis• Pneumonitis (L)
Pregnancy & Lactation	Fetal toxicities and teratogenic effects of irinotecan have been noted in animals at doses similar or less than those used in humans. Toxicities include: decreased skeletal ossification, multiple anomalies, low birth weight and increased fetal mortality. It is not known if irinotecan is excreted into breast milk but it is excreted into rat milk.

(L) Toxicity may also occur later

Formulation & Stability:

Each mL of irinotecan injection contains 20 mg irinotecan (on the basis of the trihydrate salt), 45 mg sorbitol, and 0.9 mg lactic acid. When necessary, pH has been adjusted to 3.5 (range, 3.0 to 3.8) with sodium hydroxide or hydrochloric acid. Irinotecan is available in single-dose amber glass vials in 40 mg (2 mL), 100 mg (5 mL), 300 mg (15 mL), and 500 mg (25 mL). Store at controlled room temperature 15°-30°C (59°-86°F). Protect from light. It is recommended that the vial (and backing/plastic blister) should remain in the carton until the time of use.

Guidelines for Administration:

See Treatment and Dose Modifications sections of the protocol.

IV Administration: Irinotecan must be diluted prior to infusion. Irinotecan should be diluted in D5W, (preferred) or NS to a final concentration range of 0.12-2.8 mg/mL. The solution is physically and chemically stable for up to 24 hours at room temperature (approximately 25°C) and in ambient fluorescent lighting. Solutions diluted in D5W and stored at refrigerated temperatures (approximately 2°-8°C), and protected from light are

physically and chemically stable for 48 hours. Refrigeration of admixtures using NS is not recommended due to a low and sporadic incidence of visible particulates. Care should be taken to avoid extravasation; the use of a central line is suggested.

Supplier:

Commercially available from various manufacturers. See package insert for more detailed information.

6.4 SARGRAMOSTIM

(06/26/18)

(Granulocyte Macrophage Colony Stimulating Factor, rhu GM-CSF, rGM-CSF, GM-CSF, Leukine®) NSC #613795

Source and Pharmacology:

Sargramostim (recombinant human GM-CSF) is a glycoprotein produced in yeast (*S. cerevisiae*) by recombinant DNA technology. rGM-CSF is a hematopoietic growth factor which supports survival, clonal expansion, and differentiation of hematopoietic progenitor cells. rGM-CSF induces partially committed progenitor cells to divide and differentiate in the granulocyte-macrophage pathways. rGM-CSF stimulates the production of monocytes, granulocytes, erythrocytes, and sometimes, megakaryocytes in the bone marrow. It also induces mature neutrophil and monocytes to increase phagocytosis, superoxide generation, ADCC, tumoricidal killing and cytokine production (IL-1 and tumor necrosis factor). Recombinant human GM-CSF is a glycoprotein of 127 amino acids characterized by three primary molecular masses of 15500, 16800, and 19500 daltons. The amino acid sequence differs from the natural sequence by a substitution of leucine at position 23 and the CHO moiety may be different from the native protein. After subcutaneous administration of sargramostim, peak levels were obtained in 1-4 hours and were detectable at therapeutic levels for 12-16 hours post injection. The elimination $t_{1/2}$ ranges from 1.5-2.7 hours after SubQ or IV administration.

Toxicity:

	Common Happens to 21-100 children out of every 100	Occasional Happens to 5-20 children out of every 100	Rare Happens to < 5 children out of every 100
Immediate: Within 1-2 days of receiving drug	Headache, malaise, fatigue, rash, pruritus, bone pain, myalgia, arthralgia, fever, chills	Abdominal pain, weakness, anorexia, nausea, local injection reactions	Anaphylaxis, "first dose reaction" (hypoxia, dyspnea, hypotension, fever, tachycardia, diaphoresis, flushing, back pain), vomiting, diarrhea, phlebitis, SVT, pericardial effusion
Prompt: Within 2-3 weeks, prior to the next course		Weight gain	In high doses: capillary leak syndrome: (pleural effusion, peripheral edema, ascites, weight gain, hypotension), pneumonitis, peripheral edema, elevation of creatinine, bilirubin and hepatic enzymes in patients with pre-existing renal or hepatic dysfunction
Delayed:		Thrombocytopenia	

Any time later during therapy			
Unknown Frequency and Timing:	Fetal and teratogenic toxicities: It is not known whether sargramostim can cause fetal harm or affect reproduction capacity when administered to a pregnant woman. It is unknown whether the drug is excreted in breast milk.		

Formulation and Stability:

Sargramostim is available as a lyophilized sterile, white, preservative free powder with 250 mcg (1.4 million International Units) per vial. The sargramostim reconstituted lyophilized vial contains 40 mg/mL mannitol, *USP*; 10 mg/mL sucrose, *NF*; and 1.2 mg/mL tromethamine, *USP*, as excipients. Store refrigerated at 2-8°C (36-46°F). Do not freeze or shake.

Guidelines for Administration:

See Treatment and Dose Modifications and Supportive Care sections of the protocol.

Reconstitute lyophilized powder for injection with 1 mL SWFI or 1 mL Bacteriostatic Water for Injection. **Use SWFI without benzyl alcohol for neonates, infants, and children < 2 years of age or patients with hypersensitivity to benzyl alcohol.** During reconstitution, direct the diluent at the side of the vial and gently swirl the contents to avoid foaming during dissolution. Avoid excessive or vigorous agitation; do not shake. Reconstituted solutions prepared with Bacteriostatic Water for Injection (0.9% benzyl alcohol) or the liquid preserved solution may be stored for up to 20 days following the first entry into the vial at 2°-8°C (36°-46°F). Discard reconstituted solution after 20 days have elapsed. Reconstituted solutions prepared with SWFI (without preservative) should be administered as soon as possible and within 6 hours following reconstitution.

Use sargramostim for subcutaneous injection without further dilution. Perform dilution for IV infusion in NS. If the final concentration is < 10 mcg/mL, add albumin (human) at a final concentration of 0.1% to the saline prior to addition of sargramostim to prevent adsorption to the components of the drug delivery system. For a final concentration of 0.1% albumin (human), add 1 mg albumin (human) per 1 mL NS. For example, for a final volume of 50 mL NS, add 50 mg (or 1 mL) of 5% albumin [human]. Intravenous dilutions are stable for up to 48 hours at room temperature or refrigerated but should be used within 6 hours due to microbiological concerns. Do not use an in-line membrane filter for IV infusion.

Supplier:

Commercially available. See package insert for more detailed information.

CANADIAN SITES

Sargramostim is not commercially available in Canada. Sites may purchase and import the USA commercial supply of Lyophylized Leukine® distributed by Partner Therapeutics via an International Distributor (Pharma Exports LLC; [REDACTED]

[REDACTED] under the authority of the protocol's No Objection Letter (NOL).

The Canadian Senior Medical Officer (SMO)'s office is responsible for coordinating the "Fax Back" approval with Health Canada's Biologics and Genetic Therapies Directorate for all lots for use in Canada on behalf of all Canadian sites. A list of approved lot numbers is posted on the C17 website (www.c17.ca) under the protocol titled Sargramostim. If an

unapproved lot is received from the distributor, quarantine the lot and contact the COG Canada Regulatory Affairs Office at [contact].

Canadian sites must keep a drug accountability log (DAL) and must record Lot #'s and expiry dates of shipments received and doses dispensed. Sites may use their own DAL as long as it complies with all elements of ICH GCP and Health Canada's Division 5 of the Food and Drugs Act. Each site is responsible for the procurement (import +/- purchase) of sargramostim. Sites may import and manage a single clinical trial supply for multiple protocols as long as each protocol has an NOL and the protocol the patient is registered on is recorded on the DAL.

6.5 TEMOZOLOMIDE (08/26/20)
(Temodar[®], Temodal[®]) NSC #362856

Source and Pharmacology:

An orally or intravenously administered alkylating agent, a second generation imidazotetrazine. A prodrug of MTIC, temozolomide spontaneously decomposes to MTIC at physiologic pH.

The cytotoxic effects of MTIC are manifested through alkylation (methylation) of DNA at the O⁶, N⁷ guanine positions which lead to DNA double strand breaks and apoptosis. Temozolomide is noncell cycle specific.

Temozolomide is rapidly and completely absorbed after oral administration with a peak plasma concentration (C_{max}) achieved in a median T_{max} of 1 hour. Food reduces the rate and extent of temozolomide absorption. Mean peak plasma concentration and AUC decreased by 32% and 9%, respectively, and median T_{max} increased by 2-fold (from 1-2.25 hours) when temozolomide was administered after a modified high-fat breakfast. A pharmacokinetic study comparing oral and intravenous temozolomide in patients with primary CNS malignancies showed that at 150 mg/m² dose temozolomide IV and oral capsules are bioequivalent with respect to both C_{max} and AUC of temozolomide and MTIC. Temozolomide has a mean apparent volume of distribution of 0.4 L/kg (%CV=13%). It is weakly bound to human plasma proteins; the mean percent bound of drug-related total radioactivity is 15%. Temozolomide is spontaneously hydrolyzed at physiologic pH to the active species, MTIC and to temozolomide acid metabolite. Cytochrome P450 enzymes play only a minor role in the metabolism of temozolomide and MTIC. About 38% of the administered temozolomide total radioactive dose is recovered in the urine. Overall clearance of temozolomide is about 5.5 L/hr/m². Temozolomide is rapidly eliminated, with a mean elimination half-life of 1.8 hours, and exhibits linear kinetics over the therapeutic dosing range of 75 to 250 mg/m²/day. A population analysis did not demonstrate any influence of coadministered dexamethasone, prochlorperazine, phenytoin, carbamazepine, ondansetron, H₂ receptor antagonists, or phenobarbital on the clearance of orally administered temozolomide.

The table below lists the anticipated toxicity profile of temozolomide (oral):

Incidence	Toxicities
Common (>20% of patients)	Constipation, nausea, vomiting, , anorexia, alopecia, headache, seizure, fatigue
Occasional (4-20% of patients)	Peripheral edema, skin rash, pruritus, xeroderma, erythema of skin, diarrhea, dysphagia, dizziness, ataxia, hemiparesis, asthenia, fever, stomatitis, abdominal pain, dysgeusia, weight gain, platelet count decreased, white blood cell count decreased, lymphocyte count decreased, urinary incontinence or frequency, cough, dyspnea, infection, anxiety, depression, insomnia, gait disturbance, amnesia, paresthesia, drowsiness, visual disturbances, back pain, arthralgia/myalgia
Rare (≤3% of patients)	Stevens-Johnson syndrome, toxic epidermal necrolysis, erythema multiforme, hyperbilirubinemia, transaminitis, injection site reaction (IV formulation), interstitial pneumonitis, pancytopenia (may be prolonged), myelodysplastic syndrome, leukemia secondary to oncology chemotherapy, infections and infestations – other: Pneumocystis pneumonia, pulmonary fibrosis, anaphylaxis, allergic reaction, hepatotoxicity, cholestasis, anemia, aplastic anemia
Pregnancy & Lactation	
Pregnancy Category D
 
Adequate, well-controlled studies have not been conducted in humans. Women of childbearing potential should be advised against becoming pregnant while taking temozolomide and for at least 6 months following the end of therapy. Temozolomide administration to rats and rabbits at 3/8 and 3/4 the human dose resulted in the development of malformations of the external organs, soft tissues, and skeleton. These animal studies also demonstrated embryo lethality (increased resorptions) at similar doses. There is no information available regarding the transmission of temozolomide during lactation; women should avoid breastfeeding while receiving temozolomide.

Formulation and Stability:

Temozolomide capsules are available in six different strengths (5, 20, 100, 140, 180, 250 mg). The capsules vary in size, color, and imprint according to strength. In the US, capsules are packaged in 5-count and 14-count bottles. In other countries temozolomide may be packaged in 5-count, 14-count or 20-count bottles. Temozolomide capsules are stored at 25°C (77°F); excursions permitted to 15°C to 30°C (59°F to 86°F).

Guidelines for Administration:

See Treatment and Dose Modifications sections of the protocol.

There is a potential for medication errors involving temozolomide capsules resulting in drug overdosages, which may have been caused by dispensing/taking the wrong number of capsules per day and/or product usage exceeding the prescribed dosing schedule.

When dispensing, it is extremely important that prescribing and dispensing include clear instructions on which capsules, and how many of each capsule(s) are to be taken per day. Only dispense what is needed for the course, and clearly indicate how many days of dosing the patient will have and how many days are without temozolomide dosing. When counseling patients, it is important for each patient/parent to understand the number of capsules per day and the number of days that they take temozolomide. It is also important for the patient/parent to understand the number of days that they will be off the medication.

Each strength of temozolomide must be dispensed in a separate vial or in its original container (e.g., bottle or sachet). Based on the dose prescribed, determine the number of

each strength of temozolomide capsules needed for the full course as prescribed by the physician. For example, 275 mg/day for 5 days would be dispensed as five 250 mg capsules, five 20 mg capsules, and five 5 mg capsules. Label each container with the appropriate number of capsules to be taken each day. Dispense to the patient/parent, making sure each container lists the strength (mg) per capsule and that he or she understands to take the appropriate number of capsules of temozolomide from each bottle or vial to equal the total daily dose prescribed by the physician. Institutions that have the capability to dispense temozolomide as daily doses in a blister pack may do so, taking specific precautions to ensure that the appropriate dose is provided and that the patient is educated to understand the daily dosing regimen.

For children unable to swallow the capsules whole, the oral capsules may be formulated into a suspension. To prepare a 10 mg/mL suspension triturate the contents of ten 100 mg capsules (1000 mg), 500 mg povidone K-30 and 25 mg anhydrous citric acid dissolved in 1.5 mL purified water in a glass mortar to form a uniform paste. To the paste add 50 mL of Ora-Plus® by adding a small amount, mixing, and then adding the balance. Transfer to a glass graduated cylinder. Add Ora-Sweet® or Ora-Sweet® SF to a total volume of 100 mL by rinsing the mortar with small amounts of the syrup (Ora-Sweet® or Ora-Sweet® SF). Rinse at least four times. Package in an amber plastic prescription bottle. The packaged suspension should be stored in the refrigerator at 2°-8°C (36°-46°F) for no more than 2 weeks after preparation. The suspension should be shaken well before each use. Procedures for proper handling and disposal of cytotoxic drugs should be used when preparing the suspension.⁶⁶

Extemporaneous temozolomide 10 mg/mL suspension can also be prepared using 100 mg temozolomide capsules mixed in Ora-Mix SF®. Open contents of the required number of 100 mg temozolomide capsules into a mortar and add Ora-Mix SF® until a paste forms. Add more vehicle until a liquid is formed (for each 100 mg capsule add 10 mL of Ora-Mix SF®). Transfer desired volume to a glass or polyethylene terephthalate bottle. Label the container, assigning a beyond-use-date of 30 days, for storage under refrigeration only.⁶⁷

Alternatively, the capsules can be opened and mixed with apple sauce or juice, which should be used immediately after mixing or must be used in 2 hours after mixing (refer to [Appendix VIII](#)).

Supplier:

Commercially available. See package insert for further information.

7.0 EVALUATIONS/MATERIAL AND DATA TO BE ACCESSIONED

Timing of protocol therapy administration, response assessment studies, and surgical interventions are based on schedules derived from the experimental design or on established standards of care. Minor unavoidable departures (up to 72 hours) from protocol directed therapy and/or disease evaluations (and up to 1 week for surgery) for valid clinical, patient and family logistical, or facility, procedure and/or anesthesia scheduling issues are acceptable (except where explicitly prohibited within the protocol).

7.1 End of Therapy & Follow-up

See COG Late Effects Guidelines for recommended post treatment follow-up:

<http://www.survivorshipguidelines.org/>

Note: Follow-up data are expected to be submitted per the Case Report Forms (CRFs) schedule.

STUDIES TO BE OBTAINED	End of Therapy	Disease Progression	Follow up			
			Year 1 30 days	Year 1 6 months*	Year 1 12 months*	Years 2 -5 Annually*
History	X					
Physical Exam with VS	X					
Ht, Wt, BSA	X					
Performance Status	X					
CBC, differential, platelets	X					
Electrolytes, BUN, Creatinine	X					
ALT, total bilirubin, albumin	X					
CT/MRI ¹	X ²	X				
MIBG (or FDG-PET if ¹²³ I-MIBG non-avid disease)	X ²	X				
Bilateral bone marrow aspirates and biopsies	X ²	X				
Audiogram	X		X ³		X	
Disease status	X		X	X	X	X
Toxicity/Significant events	X		X	X	X	X
Survival/Vital status	X		X	X	X	X

* +/- 2 months

1. Cross-sectional imaging should be of the original primary site and any non-osseous disease sites present at study enrollment or at time of progression.

2. For patients who experienced their first response (MR, PR, CR) at the time of the end therapy evaluation, a complete confirmatory disease evaluation should be performed *at least* 4 weeks after the end of therapy evaluation.

3. If the patient underwent an audiogram within 28 days prior to end of therapy (ie, at the end of the previous cycle), the end of therapy audiogram should be done 30 days +/- 7 days from the end of therapy date.

7.2 Research Studies for which Patient Participation is Required or Optional

See [Section 14.0](#) for Special Studies requirements. Required studies are detailed in [Section 14.1](#) and optional studies (including specimens for biobanking) are detailed in [Section 14.2](#).

A summary of specimens to be collected is provided in [Appendix X](#). Every effort should be made to obtain samples from all time points, including the pre-therapy time point. However, if the pre-ANBL1821 therapy sample cannot be obtained, subsequent samples should still be collected as specified.

8.0 CRITERIA FOR REMOVAL FROM PROTOCOL THERAPY AND OFF STUDY CRITERIA

8.1 Criteria for Removal from Protocol Therapy

- a) Progressive disease.
- b) Stable disease after 6 cycles of protocol therapy for patients enrolled prior to Amendment 4.
- c) Intolerance of study therapy or unacceptable toxicity due to protocol therapy (see [Section 5.0](#)).
- d) Refusal of further protocol therapy by patient/parent/guardian.
- e) Completion of the maximum allowable number of cycles of therapy (see [Section 4.1](#)).
- f) Physician determines it is in patient's best interest.
- g) Second malignant neoplasm (SMN).
- h) Patients who do not meet criteria to start the next treatment cycle within 21 days after the planned subsequent cycle start date (i.e. there is a ≥ 3 week delay in start of next cycle).
- i) Pregnancy.
- j) Repeat eligibility studies (if required) are outside the parameters required for eligibility (see [Section 3.2](#)).

Patients who are off protocol therapy are to be followed until they meet the criteria for Off Study (see below). Follow-up data will be required unless patient is taken off study.

8.2 Off Study Criteria

- a) Death.
- b) Lost to follow-up.
- c) Patient enrollment onto another COG study with tumor therapeutic intent (e.g. at time of progression or subsequent relapse).
- d) Withdrawal of consent for any further data submission.
- e) The fifth anniversary of the date the patient was enrolled on this study.

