1.2 Secondary Aims

1.2.1 To compare progression-free survival and overall survival between patients receiving dinutuximab, irinotecan and temozolomide with and without the addition of DFMO.

1.2.2 To define the toxicity profile of DFMO administered with dinutuximab, irinotecan and temozolomide.

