9.0 STATISTICAL CONSIDERATIONS

9.1 Sample Size and Study Duration

The proposed randomized Phase 2 study will require enrollment of 90 eligible patients, 45 assigned to each regimen. Enrollment may proceed up to 95 patients to allow up to 5% potentially ineligible patients.

Expected accrual for this study would be similar to the accrual rate of 42 patients/year observed on the ANBL1221 expansion cohort at non-Australian and New Zealand sites as the patient population and eligibility are very similar. We anticipate that given the positive results of ANBL1221 and the reality that this backbone has become widely used for first relapse, there should be similar accrual rates for this trial. Assuming this rate, the trial would take about 2.3 years to complete accrual of up to 95 patients. The study will require an additional 12 months for completion of therapy and toxicity evaluation for a total study duration of approximately 3.3 years.

The sample size may be increased if accrual is fast: specifically, if 30 months after the study commencement the average accrual rate over the previous 3 months is above an annual rate of 41 patients per year, then the study may be amended (blindly to the interim outcome data) and accrual increased to 148 eligible patients. In this case, enrollment may proceed up to 155 patients to allow up to 5% potentially ineligible patients. Assuming an accrual rate of 42 patients/year (this rate would be amended if needed based on observed accrual rate), the trial would take about 3.7 years to complete accrual and a total study duration of ~4.7 years. The amendment would be submitted after the 30-month time point so that the study will not need to be closed to accrual as a result of the increase in the target accrual.

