9.3.2 Secondary Endpoints

Progression-free survival (PFS) and overall survival (OS) will be assessed for patients receiving dinutuximab, irinotecan, and temozolomide with and without the addition of DFMO. For PFS, time to event will be calculated from the time of randomization to the occurrence of relapse, progressive disease, or death. For OS, death will be the only event considered and time to death will be calculated from the time of randomization. Patients without a PFS event or death will be censored at the time of last follow-up.

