9.3.4 Assessment of Study Objectives

The primary study aim ([1.1.1](#)) will be assessed by a one-sided continuity-corrected test of proportions with pooled variance to compare the response rates after 6 cycles in the two regimens, and the futility and efficacy monitoring rules ([Section 9.3.3](#)). The response rate by the end of 6 cycles will be calculated on each regimen, including placement of a 95% confidence interval. If a patient is a responder and later has PD or goes off protocol therapy, then the patient will be counted as a responder. If the response rate on Regimen B is significantly better, then it will be considered a therapeutic regimen worthy of further testing in patients with newly-diagnosed high-risk neuroblastoma. In addition, the response rate by the end of 6 cycles (based on confirmed responses) will also be calculated for each regimen, with responders defined as patients who achieve a confirmed minor response or better per the revised INRC⁶⁸ as their best overall response by the end of 6 cycles as determined by central review.

To address secondary objective [1.2.1](#), Kaplan-Meier curves of PFS and OS will be generated by regimen and compared using log-rank tests. PFS and OS will also be evaluated separately in the cohorts of patients enrolled prior to and post-Amendment 4 given the reduction in maximum cycles of therapy from 17 to 6 cycles.

To assess secondary aim [1.2.2](#), toxicities (Grade ≥ 3) experienced on Regimen B will be descriptively summarized.

Exploratory aim [1.3.1](#) will be assessed by exploring the relationship between response (responder vs. non-responder) after 6 cycles on Regimen B with serum cytokine levels (IL1, IL6, TNF-alpha, IFN-gamma, etc.), tumor resident immune cells (NK cells, TAMS, TILS), and critical immune cell suppressing proteins (B7H3, PDL-1) using Fisher's exact test for categorical and Wilcoxon rank-sum test for continuous factors.

To address exploratory objective [1.3.2](#), GD2 levels in tumor cells from bone marrow samples will be correlated with response (responder vs. non-responder) after 6 cycles using Fisher's exact test for categorical and the Wilcoxon rank-sum test for continuous factors.

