12.0 STUDY REPORTING AND MONITORING

The Case Report Forms and the submission schedule are posted on the COG web site with each protocol under “*Data Collection/Specimens*”. A submission schedule is included.

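### Entry to another COG therapeutic study ends required vital-status collection under 8.1 and 8.2(c), and only the general censoring rule in 9.3.2 covers these exits in the OS analysis

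*Combined protocol and SAP*

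**What the plan says.** Comparing OS between the regimens is part of a secondary aim (section 1.2.1): "To compare progression-free survival and overall survival between patients receiving dinutuximab, irinotecan and temozolomide with and without the addition of DFMO". Section 7.1 schedules survival and vital status at end of therapy, at 30 days, 6 months and 12 months, and annually in years 2 to 5, and adds: "Follow-up data are expected to be submitted per the Case Report Forms (CRFs) schedule". That schedule is held elsewhere (section 12.0): "The Case Report Forms and the submission schedule are posted on the COG web site with each protocol".

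Section 8.1 follows patients who have stopped protocol therapy until they meet an off-study criterion: "Follow-up data will be required unless patient is taken off study". Section 8.2 lists five such criteria. Item (c) is "Patient enrollment onto another COG study with tumor therapeutic intent (e.g. at time of progression or subsequent relapse"). Item (d), withdrawal of consent for further data submission, is separate, and item (e) is the fifth anniversary of enrollment.

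For the analysis, section 9.3.2 says: "Patients without a PFS event or death will be censored at the time of last follow-up". Section 9.3.4 says: "Kaplan-Meier curves of PFS and OS will be generated by regimen and compared using log-rank tests". It also evaluates PFS and OS separately in patients enrolled before and after Amendment 4.

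Section 3.1.1 gives each patient one COG ID for all later dealings with COG. It also says that patients are to be offered a COG registry and outcome study.

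**The concern.** Kaplan-Meier and log-rank methods assume that a censored patient has the same outlook as those still at risk. A patient who leaves under 8.2(c) may do so because the tumor has progressed, which is the protocol's own example. The general rule in 9.3.2 then censors OS at about the time when the risk of death changes, and later deaths are not required to be recorded for this trial.

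Two things are at stake: deaths missing from a 90-patient trial, and an absolute OS estimate that may be too high or too low. The loss would weigh more in the two Amendment 4 cohorts, which are smaller. Item (c) is also not limited to progression, so a patient who transfers without progression would have PFS follow-up cut short as well.

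**Working it through.** **The text.** Vital status is a follow-up item (7.1). Follow-up data are required until off study (8.1). Entry to another COG therapeutic study is off study (8.2(c)). So required collection can end before 8.2(e). Sections 9.3.2, 9.3.4 and 10.2.5 contain no exception for these exits, and 3.1.1 does not tie the COG ID or the registry to this trial's OS.

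**The plan's own figure.** There is no OS power, event count or loss allowance to reproduce. The primary sample size does reproduce. With 40% against 60%, one-sided alpha 0.20 and 80% power, both normal quantiles are 0.8416:

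- Uncorrected: [0.8416 × (√0.50 + √0.48)]² / 0.20² = 34.7 per arm.
- Continuity-corrected: (34.7/4) × [1 + √(1 + 4/(34.7 × 0.20))]² = 44.1, so 45 per arm and 90 in total.

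The point below does not enter this calculation.

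**Illustration of the OS bias.** The documents give neither the share q of progressors who transfer nor the ratio h of their death hazard to that of other progressors. Both are assumed: q from 5% to 50%, h from 0.3 to 1.5, transfer at progression, exponential times. The medians (PFS 13.3, time to progression 19.8, OS 36.2 months) come from the 24-patient Phase 1 study of a different DFMO regimen in section 2.4.

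- Total PFS hazard: λ = ln2/13.3 = 0.0521 per month.
- Progression hazard: p = λ in Model A (every PFS event is a progression); p = ln2/19.8 = 0.0350 in Model B (the remainder is death without progression).
- Progressed and alive at t, with later hazard m: P(t; m) = p(e^(-mt) - e^(-λt))/(λ - m).
- True OS: S(t) = e^(-λt) + (1-q)P(t; μ) + qP(t; hμ), with μ chosen so that S(36.2) = 0.5. At h = 1, μ is 0.0415 (A) or 0.0219 (B).
- Kaplan-Meier limit at 36 months: exp of minus the integral from 0 to 36 of [(λ-p)e^(-λt) + μ(1-q)P(t; μ)] / [e^(-λt) + (1-q)P(t; μ)].

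True 36-month OS is 50.3% (A) or 50.2% (B). Worked case, Model A, q = 25%, h = 1: Kaplan-Meier 55.1% against 50.3%, a bias of +4.8 points. All cases, Kaplan-Meier minus truth in points:

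| Model | h | q=5% | 10% | 25% | 50% |
|---|---|---|---|---|---|
| A | 1.5 | +1.4 | +2.8 | +7.3 | +16.3 |
| A | 1 | +0.8 | +1.7 | +4.8 | +12.0 |
| A | 0.5 | -0.1 | -0.1 | +0.5 | +4.8 |
| A | 0.3 | -0.6 | -1.2 | -2.3 | 0.0 |
| B | 1.5 | +0.4 | +0.9 | +2.0 | +3.4 |
| B | 1 | +0.1 | +0.2 | +0.5 | +1.2 |
| B | 0.5 | -0.4 | -0.7 | -1.7 | -2.6 |
| B | 0.3 | -0.6 | -1.2 | -3.0 | -5.2 |

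**Unrecorded deaths among 90 patients.** The expected number by t is 90q[(p/λ)(1 - e^(-λt)) - P(t; hμ)]. At h = 1 and q = 10%, 25% and 50%:

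- 60 months for all: 6.9, 17.2 and 34.4 of 68.8 (A); 3.4, 8.6 and 17.2 of 62.6 (B).
- Cut-off at the planned end, "for a total study duration of approximately 3.3 years", with uniform accrual over 2.3 years: 3.0, 7.5 and 15.0 of 30.0 (A); 1.3, 3.2 and 6.4 of 33.9 (B).

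**Between arms (h = 1).** Multiply all hazards in one arm by 0.7 and let the same share transfer in both. A true 36-month difference of 17.1 points (A) shows as 16.9, 16.5 and 15.1 at 10%, 25% and 50% transfer; a true 12.2 (B) shows as 12.2, 12.1 and 12.0. With no true difference but 10% transferring in one arm and 40% in the other, a spurious gap of 7.0 (A) or 0.7 (B) points appears.

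**The case against.** The strongest reply has four parts, and most of it stands.

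- A reader might infer that the plan has no OS rule for these patients. It has one: 9.3.2 covers them by default. What is missing is a rule specific to these exits, or a statement that vital status will be obtained from the later study.
- A reader might infer that progressors in general leave follow-up. They do not. Those treated off study or on non-COG trials remain in follow-up to year 5.
- A reader might infer that the OS comparison is biased for or against DFMO. The documents do not support that. Equal transfer barely moves the difference, a spurious gap needs unequal transfer, and nothing in the documents gives a reason to expect it. OS is secondary and unpowered.
- Section 8.1 removes a requirement; it does not forbid collection. The CRF schedule is outside the documents and may already cover this, and the registry and outcome study offered under 3.1.1 might hold the dates. This cannot be checked here, and neither source is tied to this trial's OS.

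The size is also open to challenge. It rests on an assumed transfer share, an assumed hazard ratio and borrowed medians. At 50% transfer and equal hazard, the choice of model alone moves the bias from +12.0 to +1.2 points.

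**Conclusion.** The point holds as a gap in required data collection and in the OS rule. Under 8.1 with 8.2(c), deaths after entry to another COG therapeutic study need not be recorded, and the general censoring rule treats those exits as non-informative.

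The size and sign of the resulting bias in the OS level cannot be determined from the documents. The illustrative range of about -5 to +16 points is not a bound: it depends on 5% to 50% transfer, a hazard ratio of 0.3 to 1.5, the two models and the borrowed medians, and its extremes come from the 50% column. The more dependable result is that deaths are lost in every case counted.

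The consequence is limited to the absolute OS level and to lost OS events. The primary response endpoint and the sample size of 90 are unaffected. The change is worth making because it is cheap and because deaths not collected prospectively may be hard to recover.

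**What to change.** Amend 8.2(c) so that entry to another COG therapeutic study does not end collection of date of death or date last known alive, obtained directly or by COG ID linkage, up to the fifth anniversary, unless consent for data submission is withdrawn under 8.2(d). State in 9.3.2 that OS is not censored at that event. If the CRF schedule or an existing COG linkage already provides these dates, a sentence in 8.2 saying so is enough. Reporting the number of 8.2(c) exits by arm would help but is optional.

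The cost is a small amendment and a little extra data collection or linkage: vital status is already scheduled to year 5, and the COG ID already identifies the patient. Treatment, eligibility and the primary analysis do not change.
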